9.2. Variables

[figure not shown]
From the final sample, the following measures will be reported (Figure 2):

1. Patients with a claim for the respective treatment (apixaban for apixaban cohort or warfarin for warfarin cohort; using NDC from LRx) as their first post-discharge outpatient treatment (on or within 30 days following discharge i.e. discharge date or ≤ 30 days after discharge date) (n, %). These patients will comprise the analytic cohort for outcomes assessment.

- a. The date of the first post-discharge outpatient prescription claim in LRx (apixaban or warfarin) will be defined as the ‘treatment index date’ for patients in both cohorts respectively.
 - b. Patients will be required to have pharmacy stability during the 6-month period preceding the treatment index date, defined as consistent reporting of data in each month from the pharmacy associated with the treatment index date in LRx to ensure continuous visibility within LRx. The number of patients excluded due to lack of stability will be reported (n, %)
 - c. Patients with recurrent VTE, major bleeding, or CRNM bleeding between the discharge date and the treatment index date will be excluded. The number of patients excluded due to these reasons will be reported (n, %).
 - d. Patients will be followed from the treatment index date until the earliest of last prescription, last patient medical claim, end of pharmacy stability, or end of study period using the Dx/Rx databases.
2. Patients with OAC (warfarin, apixaban, rivaroxaban, dabigatran, or edoxaban) other than the respective inpatient treatment as their first outpatient prescription claim (on discharge date or within 30 days of discharge) (NDC codes from LRx; n, %). These patients will be captured as having switched from inpatient therapy and will not be further evaluated for outcomes.
 3. Patients with no post-discharge outpatient prescription claim for any OAC (on or within 30 days of discharge) (NDC from LRx; n, %)

All study outcomes will be evaluated for the apixaban and warfarin cohorts.

Figure 2. Study Flow

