9.2.2. Outcome measures

The following outcome measures are assessed post-discharge, and will be measured during the variable post-index period starting on the treatment index date for the apixaban and warfarin cohorts.

Treatment patterns

- Persistent days (mean, SD, median, IQR, min, max) will be reported for patients until they discontinue, switch or end of follow-up based on definitions below
- Patients discontinuing outpatient treatment of apixaban or warfarin, respectively (NDC codes from LRx; n, %)

Note: Discontinuation will be defined as the occurrence of a ≥ 30 day gap from the run-out of days' supply of the treatment (post-discharge) index prescription (i.e. apixaban or warfarin) to the date of the next claim for the respective therapy or with no other claims for the respective therapy. The date of the discontinuation will be defined as the last day of the days' supply of the last filled prescription.

- Time (in days) from treatment index date to discontinuation date (mean, SD, median, IQR, min, max)

Note: Kaplan-Meier (KM) curves will be generated to measure median time (and 95 % CI) to discontinuation.

- Patients switching to an OAC other than apixaban or warfarin, respectively (switched) (NDC codes from LRx; n, %)

Note: Patients will be considered to have switched if they filled a prescription for OAC other than apixaban or warfarin, respectively (identified through NDC codes in LRx) or for PAC within 30 days before or after the run out date of index treatment. The date of the switch will be defined as date of the prescription of such a therapy (OAC or PAC).

- Time (in days) from treatment index date to switch date, defined as the date of the first claim for the new OAC or PAC (mean, SD, median, IQR, min, max)

Note: KM curves will be generated to measure median time (and 95 % CI) to switching

Clinical Outcomes

The following clinical outcomes will be assessed during the time patients are persistent with their respective index apixaban or warfarin treatment (treatment index):

- Patients with ≥ 1 hospitalization for recurrent VTE (ICD-10 codes in CDM; n, %)
- Incidence rate (IR) of recurrent VTE (per 100 patient years)
 - The date of the first observed event will be flagged. The numerator for IR will be the number of patients with the event of interest and denominator will be the ‘at risk’ period i.e. the time to first event. The 95% confidence intervals (CI) will also be reported.

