Note: Recurrent VTE will be defined as inpatient hospitalization with a primary diagnosis of VTE occurring 7 or more days after the first hospitalization discharge date.

- Time (days) from first hospitalization discharge date to first recurrent VTE hospitalization (mean, SD, median, IQR, min, max)
- Time (days) from treatment index date to first recurrent VTE hospitalization (mean, SD, median, IQR, min, max)
- Patients with ≥ 1 hospitalization for major bleeding (ICD-10 codes in CDM; n, %)
- IR of major bleeding (per 100 patient years)

Note: Major bleeding will be defined as inpatient hospitalization with primary diagnosis of gastro-intestinal bleeding, intracranial hemorrhage (ICH) or other major bleeding

- Time (days) from first hospitalization discharge date to first major bleeding episode (mean, SD, median, IQR, min, max)
- Time (days) from treatment index date to first major bleeding episode (mean, SD, median, IQR, min, max)
- Patients with ≥ 1 CRNM bleeding event (n, %)
- IR of CRNM bleeding (per 100 patient years)

Note: CRNM bleeding will be defined as inpatient hospitalization with a secondary diagnosis code for bleeding (without a major bleeding code in the primary position) or an outpatient encounter with a diagnosis code in any position for CRNM GI bleeding or other non-critical types of bleeding. Specifically, it is defined as:

(1) An inpatient admission with a secondary diagnosis for “noncritical site” bleeding such as GI bleeding or other selected noncritical types/sites of bleeding (excluded if major bleeding occurred during the same hospitalization), OR

(2) An outpatient encounter with a diagnosis code for GI bleeding and other selected noncritical types/sites of bleeding.

Any CRNM bleeding events (as described above) that follow a major bleeding event (described above) will not be included in the analysis of CRNM bleeding

- Time (days) from first hospitalization discharge date to first CRNM bleeding episode (mean, SD, median, IQR, min, max)
- Time (days) from treatment index date to first CRNM bleeding episode (mean, SD, median, IQR, min, max)

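### Follow-up ends at the last Dx or LRx record, so CDM admissions for recurrent VTE or major bleeding that are fatal or end a patient's claims are selectively lost

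*Combined protocol and SAP*

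**What the plan says.** Section 9.2, item 1d, starts follow-up at treatment index and keeps it open "until the earliest of last prescription, last patient medical claim, end of pharmacy stability, or end of study period using the Dx/Rx databases". CDM is not among the databases named.

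Section 9.2.2 has the clinical outcomes "assessed during the time patients are persistent with their respective index apixaban or warfarin treatment". It also says that persistent days "will be reported for patients until they discontinue, switch or end of follow-up based on definitions below". Item 1d therefore caps the window in which clinical events can be counted.

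Two of the three clinical outcomes are tied to CDM: "hospitalization for recurrent VTE (ICD-10 codes in CDM; n" and "hospitalization for major bleeding (ICD-10 codes in CDM; n" (each entry goes on to a percentage). For the incidence rate, "The numerator for IR will be the number of patients with the event of interest and denominator will be the" time at risk up to the first event.

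Other relevant statements:
- Section 9.3 describes inpatient data in Dx as limited.
- Section 9.8 says that mortality is not available.
- Section 9.1.1 reads in-hospital death from the CDM discharge disposition, but only for the index stay.
- Section 9.6 plans Cox models for the clinical events, with treatment cohort as the main effect and warfarin as reference.

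No section says whether 'last prescription' means any drug or the index drug, or a fill date or the end of supply.

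**The concern.** The outcome is looked for in one database and the clock is stopped by two others. Because item 1d takes the earliest of its terms, whether an admission is counted depends on what the patient does afterwards. A patient who has a bleed, goes home, fills a prescription and sees a physician keeps the event. A patient who dies during the admission usually has no later fill, so follow-up has already closed when the event occurs.

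That is outcome-dependent censoring, and it removes the gravest events first. Objective 3 is the only objective that concerns recurrence and bleeding. Its incidence rates would be too low, and a reader could not tell by how much. Section 9.8 does not list this loss among the limitations.

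**Working it through.** The protocol gives no event rate, case fatality or power figure on this point, so there is nothing to reproduce. The check is logical first, then arithmetic under stated assumptions.

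**1. Condition for counting an event.** Let E be the admission date, R the last prescription date and D the last Dx claim date. Item 1d gives end of follow-up ≤ min(R, D). Persistent time cannot run past end of follow-up, so E is counted only if R ≥ E and D ≥ E.

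**2. Example (illustrative days).** The index drug is filled on day 60 with 30 days' supply, so supply lasts to about day 60 + 30 = 90. A fatal CDM admission for bleeding occurs on day 72. The patient is on supply, since 72 < 90.
- *Fill-date reading, any drug or index drug:* with no fill on or after day 72, R < 72 and the event is dropped. A Dx claim from the stay does not help, because R already fails.
- *End-of-supply reading:* R is about day 90, so R ≥ 72. The event counts only if D ≥ 72, that is, only if the stay produces a Dx claim.

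**3. Size of the rate bias.** Let f be the share of on-treatment events that are terminal (fatal, or ending the patient's claims). Events are rare, so person-time hardly changes.
- Fill-date reading: observed rate ≈ (1 − f) × true rate. At an assumed 5 per 100 patient-years: f = 0.05 gives 0.95 × 5 = 4.75; f = 0.10 gives 0.90 × 5 = 4.50; f = 0.20 gives 0.80 × 5 = 4.00.
- End-of-supply reading: if a share p of terminal stays yields a Dx claim dated on or after admission, the loss is about f × (1 − p). It lies between 0 (p = 1) and f (p = 0). The documents give neither f nor p.

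**4. Simulation as a consistency check** (fill-date reading, any drug). All inputs are assumed: 2,000,000 patients per scenario, 30-day fills, other prescriptions and Dx claims about every 30 days, mean time on drug about 300 days, administrative end at 60 to 365 days. Rates are per 100 patient-years.

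| Assumed rate | f | Rate with at-risk time to run-out or administrative end | Rate under item 1d | Loss |
|---|---|---|---|---|
| 5 | 0 | 5.01 | 5.02 | none |
| 5 | 0.1 | 5.01 | 4.53 | 1 − 4.53/5.01 = 9.6% |
| 5 | 0.2 | 4.98 | 3.97 | 1 − 3.97/4.98 = 20.3% |
| 5 | 0.3 | 4.98 | 3.46 | 1 − 3.46/4.98 = 30.5% |
| 2 | 0.1 | 1.99 | 1.80 | 1 − 1.80/1.99 = 9.5% |
| 2 | 0.2 | 2.01 | 1.60 | 1 − 1.60/2.01 = 20.4% |
| 2 | 0.3 | 2.03 | 1.42 | 1 − 1.42/2.03 = 30.0% |

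The f = 0 row separates the causes. Item 1d still shortens follow-up there (36,199 of 41,466 events counted at rate 5), but the rate is unbiased because person-time shrinks in step. The bias comes from the terminal events. Giving every terminal stay its own Dx claim changed nothing, because the last fill still preceded the event.

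**5. Hazard ratio.** Observed HR ≈ true HR × (1 − f for apixaban)/(1 − f for warfarin).
- Equal shares: factor 1.
- 0.1 and 0.2: 0.9/0.8 = 1.125. Reversed: 0.8/0.9 = 0.889.
- 0.1 and 0.3: 0.9/0.7 = 1.286. Reversed: 0.7/0.9 = 0.778.

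**The case against.** **'Last prescription' may mean end of supply.** Section 9.2.2 dates discontinuation at the end of the last fill's supply, so this reading is plausible. A reader might infer that fatal events can never be counted, but the text does not support that. On the end-of-supply reading a fatal stay with a Dx claim is kept, and on any reading a fill and a Dx claim on or after the admission date rescue the event. What remains is that the term is undefined, one natural reading loses terminal events, and the other makes their capture depend on a database with limited inpatient data.

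**The loss could be made to look much larger.** A reader might take 'last prescription' as the last index-drug fill date. Then events after which the drug is not refilled are lost too. With an assumed 10% fatal and 40% stopping, a rate of 4.0 per 100 patient-years would fall to 4.0 × (1 − 0.50) = 2.0. Section 9.2.2 makes this reading unlikely: a final discontinuation is recognised by a 30-day gap after run-out, and it could not be observed if follow-up closed at the last index fill. The primary treatment-pattern endpoint would fail. Such figures should not be used.

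**The simulation returns its own assumption.** This stands. Terminal events were set to end all claims, so zero were counted by construction. The simulation confirms the arithmetic and says nothing about the true f.

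**A biased hazard ratio might be inferred.** The documents do not show one. With equal terminal shares the factor is 1, and nothing in the protocol says which cohort would have the larger share.

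**Last-activity censoring is a reasonable visibility proxy in open claims.** Sections 9.3 and 9.8 disclose that enrollment cannot be verified and that mortality is missing. That explains the rule, but it does not disclose that capture depends on the severity of the event. Deaths outside CDM hospitals would be missed under any rule.

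**Conclusion.** The concern holds in a limited form. Item 1d closes follow-up from Dx and LRx records, while recurrent VTE and major bleeding are CDM admissions. On-supply admissions that are fatal or end the patient's claims are therefore selectively lost, and no other section repairs this.

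On the fill-date reading, incidence rates are low by about the terminal share, for example 5-20% if 5-20% of events are terminal. On the end-of-supply reading the loss is smaller, to the extent that such stays generate Dx claims. The terminal share is an assumption throughout. An effect on the hazard ratio is possible only if the shares differ between cohorts, and its direction cannot be derived.

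The point applies fully to recurrent VTE and major bleeding. CRNM bleeding is only partly exposed: its definition includes outpatient encounters, and no source database is named for it.

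Severity: should-fix. Objective 3 is secondary, and Section 9.6 names treatment patterns as the primary endpoint.

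**What to change.** For the CDM-based clinical outcomes:

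1. End at-risk time at the earliest of first event, run-out or discontinuation of index supply, switch, end of pharmacy stability, or end of the study period. Do not censor at last prescription or last medical claim.
2. Apply this to every patient, with or without an event. Extending follow-up only for patients with a CDM admission would add events without the matching person-time and bias rates upward.
3. State that a qualifying CDM admission in that window counts even if it is the patient's last record in any database.
4. Define 'last prescription': which drug, and fill date or end of supply.
5. Report how many events the change adds, and how many of them have an expired discharge disposition in CDM.
6. Keep the current last-claim rule as a sensitivity analysis, and list the issue in Section 9.8.

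Record the change formally. Section 9.6 promises an amendment only for major changes to the primary endpoint, so a programming repair here could otherwise go undocumented.

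The cost is protocol wording and a small programming change on data already linked. The real downside is up to one fill's days' supply of person-time per patient (as much as about 90 days if fills are that long; the protocol gives no fill length) with no later claim to confirm visibility. Admissions to hospitals outside CDM stay unseen in that time, which could itself lower rates somewhat. The sensitivity analysis shows how much the choice matters.

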9.1.1. Inclusion criteria

Patients must meet all of the following inclusion criteria to be eligible for inclusion in the study:

1. Patients with an inpatient hospitalization with admit date and discharge date between 01 January 2018 and 30 November 2022 (selection window) in CDM with a primary diagnosis of VTE

Note: The admit date of the first hospitalization with primary diagnosis of VTE during the selection window will be flagged. Only patients with overnight stays with discharge date after the admit date (to confirm inpatient stay with overnight admission) will be included in the study.

Note: Number of patients who died during hospitalization (identified from discharge disposition measure) will be reported and these patients will be excluded from the study.

2. With evidence of receiving apixaban or warfarin during the hospitalization

Note: The date of the record with first apixaban or warfarin administration during the hospitalization will be flagged as the start of apixaban or warfarin treatment. Patients will be assigned to the apixaban or warfarin cohort based on this treatment received during hospitalization.

3. With linkage to LRx between 01 July 2017 and 31 December 2022 (i.e. study period)
4. With linkage to Dx during the study period
5. With activity in the 6 months prior to the admit date of hospitalization, defined as ≥ 1 claim in Dx and ≥ 1 prescription claim in LRx (pre hospitalization period)
6. With activity in the 1-month after the discharge date of hospitalization, defined as ≥ 1 claim in Dx and ≥ 1 prescription claim in LRx (variable post hospitalization period)
Note: Patients will have a minimum 1-month post discharge period (to capture outpatient treatment)
7. With age ≥ 18 years on apixaban or warfarin administration date during index hospitalization

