9.2.1. Baseline Measures

Baseline demographic, hospitalization and clinical characteristics will be assessed for the apixaban and warfarin cohorts, specifically among patients with their first outpatient index prescription (i.e. treatment index date) and with pharmacy stability. Demographic features will be measured on the patient’s treatment index date. Clinical characteristics will be assessed during the 6-months prior to the treatment-index date. Index hospitalization characteristics will also be assessed and reported for the apixaban and warfarin cohorts.

Baseline demographic characteristics (using LRx data)

- Age (years; mean, standard deviation [SD], median, interquartile range (IQR), min, max)
- Age group (18-34, 35-44, 45-54, 55-64, ≥65 years; n, %)
- Gender (male, female; n, %)
- Payer type (Third party, Medicaid, Medicare, Medicare part D, cash, other; n, %)
- Index date year (2018, 2019, 2020, 2021, 2022; n, %)

090177e19cc79c7fApproved\Approved On: 03-Mar-2023 00:48 (GMT)

- Follow-up duration (mean, SD, median, IQR, min, max)

Hospitalization characteristics (using CDM data)

- Hospital geographic region (Northeast, Midwest, South, West)
- Number of hospital beds (1-99 beds, 100-199 beds, 200-299 beds, 300-499 beds, 500+ beds)
- Hospital location (Rural, Urban)
- Teaching status (Teaching, Non-teaching)
- Admitting source (ER, referral and transfer, routine admission, other, unspecified)
- Discharge disposition (Alive – Home, Left Against Medical Advice or Discontinued Care [LAMA], Transferred – Long Term Care, Transferred – Other Institution, Transferred – Short-Term Hospital, Unknown/Other)
- Index VTE type (DVT only, PE only, DVT and PE; n, %).
- VTE etiology: (Provoked: VTE preceded by hormone therapy, fracture/trauma involving lower extremities, pelvic/orthopedic surgery, or hospitalization for any reason for ≥ 3 days during 3 months prior to index VTE event. Unprovoked: VTE events not classified as provoked)

Baseline clinical characteristics

- Prescribing provider specialty associated with the treatment index prescription in LRx (primary care [general practice/family practice/internal medicine/physician assistant/nurse practitioner], cardiologist, other, unknown; n, %) (Frequency table will be provided with details on provider specialty counts within ‘other’ category)
- Charlson Comorbidity Index (CCI, Dartmouth-Manitoba adaptation; mean, SD, median, IQR, min, max)
- CCI (categorical [0-1, 2, 3, 4+]); n, %)

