IQVIA's Dx database captures over one billion pre-adjudicated claims and three billion records obtained annually from approximately 800,000 office-based physicians and specialists. Dx database is updated on a weekly basis with approximately a 30-60 day lag for data completeness. Key information includes International Classification of Diseases, ninth revision, clinical modification (ICD-9-CM) and International Classification of Diseases, tenth revision, clinical modification (ICD-10-CM) diagnoses, CPT/procedure/Healthcare Common Procedure Coding System (HCPCS) for medical conditions and procedures, date of service, location of care, (pre-adjudicated) charged amount for service, payer types (commercial, Medicaid, Medicare, cash payment), patient age and sex. Note that inpatient data is limited.

Longitudinal Prescription Claims (LRx)

IQVIA LRx database captures information on dispensed prescriptions sourced from retail, mail, long-term care, and specialty pharmacies. These suppliers have direct, long-standing relationships with IQVIA, with many providing data on a daily basis, and all suppliers support weekly data feeds with an ability to provide insight within ten days of the end of each week. This enables IQVIA to ensure that the LRx database has good longitudinal, representative, and current data from consistent and stable suppliers. IQVIA has industry-leading coverage in the following channels: 92% coverage of the retail channel, 72% coverage of standard mail service, and 76% of long-term care facilities. IQVIA receives specialty data directly from the pharmacy resulting in near census data coverage, contributing to greater precision for longitudinal analysis. Additionally, diagnosis is included directly on the majority of specialty pharmacy transactions from the specialty pharmacy providers. An important strength of the LRx database for this analysis is the longitudinal capture of adjudicated and cash prescriptions for all age categories, regardless of insurance type.

Linkage Methodology

A proposed dataset will be constructed utilizing patient data from LRx, Dx and CDM, with the appropriate dataset being selected based upon proportion of linked patients. This process which is compliant with The Health Insurance Portability and Accountability Act of 1996 (HIPAA) is described below:

- IQVIA has developed a patented and proprietary encryption algorithm that utilizes actual patient-level information to create a unique Patient identifier (ID)⁸

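### The 30-day fill measure does not separate transferred patients, so the group with no OAC claim can mix anticoagulant supplied inside a facility with true non-filling; net direction and size are unknown.

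*Combined protocol and SAP*

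**What the plan says.** Section 9.2 divides the final sample into three groups by the first LRx claim from the discharge date to day 30: the same drug as in hospital, a different OAC, or none. The third group is "Patients with no post-discharge outpatient prescription claim for any OAC". The Outcomes list in the Abstract (Section 4) presents this result as post-discharge continuity, that is, as persistence, discontinuation or switching.

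One discharge disposition leads to exclusion. Section 9.1.1 states: "Number of patients who died during hospitalization (identified from discharge disposition measure) will be reported and these patients will be excluded from the study". No criterion in Sections 9.1.1 or 9.1.2 deals with transfers. The data do identify them, since Section 9.2.1 lists "Transferred – Long Term Care, Transferred – Other Institution, Transferred – Short-Term Hospital, Unknown/Other" among the disposition codes. That section introduces its characteristics as assessed "specifically among patients with their first outpatient index prescription (i.e. treatment index date) and with pharmacy stability", then adds that index hospitalization characteristics will be reported for the two cohorts. It does not plan fill status by disposition.

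Section 9.3 gives the LRx sources as retail, mail, long-term care and specialty pharmacies, with coverage of "76% of long-term care facilities" in the long-term care channel. Inclusion criterion 6 requires at least one Dx claim and at least one LRx claim, for any drug, in the month after discharge.

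**The concern.** A patient who moves from the index hospital to another facility may be anticoagulated throughout the 30 days without generating an outpatient claim. Drug given during a stay at a receiving hospital is not among the LRx sources that Section 9.3 names, and 24% of long-term care facilities are outside LRx. If such a patient has one other prescription in LRx and one Dx claim that month, the plan retains the patient and counts no OAC claim. A patient who leaves the facility and fills after day 30 is counted the same way. Neither can be told apart from someone who went home and stopped.

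The share with no OAC claim is a main result under Objective 2. Section 7 itself gives as motivation that regimen or setting may affect continuation after discharge. If the cohorts differ in how often patients are transferred, their percentages would also differ for reasons unrelated to treatment. The documents give no transfer share for either cohort, so that last point is conditional.

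**Working it through.** The plan states no continuation rate and no transfer share, so there is no figure to reproduce. The check is a misclassification calculation on assumed inputs. For simplicity, a continuer is a patient truly on OAC in the 30 days, and switching is ignored.

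**Inputs**
- c = true continuation, assumed 80% in home-discharged and transferred patients alike.
- t = share of patients transferred, assumed 15%, with 5% to 30% as the range.
- h = share of transferred continuers whose OAC supply is not seen in LRx. The low value of 24% is 100% minus the 76% long-term care coverage in Section 9.3. Applying it to all transfers is an assumption. The higher values of 50% and 100% are assumed.
- r = share of those unseen continuers who still pass criterion 6 through another LRx claim, taken from 0 to 1.
- q = share of true non-continuers with no LRx claim, whom criterion 6 removes (unknown).

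**Step 1: the facility-supply mechanism alone (q = 0).**
Measured continuation = (c − t·c·h) / (1 − t·c·h·(1 − r)).

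With t = 15%, the unseen share t·c·h is 0.15 × 0.80 × 0.24 = 0.0288, or 0.15 × 0.80 × 0.50 = 0.0600.

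| h | all pass criterion 6 (r = 1) | none pass (r = 0) |
|---|---|---|
| 24% | 0.7712 / 1 = 77.1%, down 2.9 points | 0.7712 / 0.9712 = 79.4%, down 0.6 |
| 50% | 0.7400 / 1 = 74.0%, down 6.0 points | 0.7400 / 0.9400 = 78.7%, down 1.3 |

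At r = 0 nobody is misclassified. The small drop arises because criterion 6 has removed true continuers from the sample.

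**Step 2: range over the transfer share.** With h = 24% and t from 5% to 30%, the drop is 1.0 to 5.8 points if all affected patients pass and 0.2 to 1.2 if none do. With h = 100% and all passing, it is 4 to 24 points (0.05 × 0.80 = 0.04; 0.30 × 0.80 = 0.24).

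**Step 3: criterion 6 acting on true non-fillers.** With no facility effect, measured continuation = c / (1 − (1 − c)·q). For q = 10%, 25% and 50% this gives 81.6%, 84.2% and 88.9%, which are overstatements.

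**Step 4: both together.** Measured continuation = (c − t·c·h) / (1 − t·c·h·(1 − r) − (1 − c)·q). With t = 10%, h = 50%, r = 50% and q = 25%: 0.76 / (1 − 0.02 − 0.05) = 0.76 / 0.93 = 81.7%, above the true 80%.

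The result is an understatement only if t·c·h·(1 − c(1 − r)) exceeds c(1 − c)·q. At t = 15% and h = 50%, that requires q below 0.06 / 0.16 = 37.5% when r = 1, or below 0.06 × 0.2 / 0.16 = 7.5% when r = 0. The documents give neither q nor r, so the sign is open.

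**The case against.** The strongest reply is inclusion criterion 6. The Section 9.2 measures are taken from the sample left after that filter, so a patient supplied entirely inside a facility, with no LRx claim, is removed and not counted as a non-filler. The error needs a narrower patient: OAC unseen but some other drug seen in the same month. If one supplier provides all of a resident's drugs, that group could be small. LRx also covers most long-term care facilities, Section 9.8 already warns of lost visibility at non-contributing sites, and Section 9.1.2 allows criteria to be revisited after the attrition table.

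Much of this stands. A reader might infer that every transferred patient stays in the denominator and that continuation is therefore understated. The documents do not support that, because criterion 6 removes some transferred patients and also removes true non-fillers, which pushes the figure up. A reader might also multiply 15% by 24% and 50% to get 3.6 to 7.5 points. That treats every transferred patient as a true continuer who passes criterion 6, and the products are points of the whole sample, not of the group without an OAC claim. Nor is it certain that disposition will be described only among patients who filled, since the wording of Section 9.2.1 is ambiguous.

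The reply does not remove the core. Criterion 6 accepts a claim for any drug, so a statin refill plus a Dx claim keeps a facility-supplied patient in the sample. The general limitation does not mention drug supplied during a facility stay. Even on the wider reading of Section 9.2.1, one overall distribution of disposition would not show fill status by disposition.

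**Conclusion.** The concern holds in limited form. The 30-day classification counts LRx claims only, from CDM discharge, for every patient discharged alive who meets the criteria, and has no disposition stratum. The group without an OAC claim can therefore combine unseen facility supply, late fills after a facility stay, and true non-filling, while the Abstract presents the result as continuity of treatment.

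Taken alone, the mechanism lowers measured continuation: by 2.9 to 6.0 points if all affected patients pass criterion 6, and by 0.6 to 1.3 points if none do. Those figures assume 15% transferred, 80% true continuation in every disposition, and 24% to 50% of transferred patients' supply unseen. They are illustrations and not estimates for this study. Net understatement is not established, and neither is a difference between cohorts. Two opposing effects of unknown size are a reason to show the result by disposition, where a reader can judge them.

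**What to change.** Keep the all-patient figure as the main result, because Objective 2 concerns everyone started on apixaban or warfarin in hospital. Then:

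1. Report the three Section 9.2 fill categories by discharge disposition within each cohort: home, each transfer category, left against medical advice, and unknown/other.
2. Add a sensitivity analysis limited to patients discharged alive to home.
3. In the attrition table, report by disposition how many patients criterion 6 removes.
4. In Section 9.8, name drug supplied inside a receiving facility as a limitation of the fill measure.

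Two other remedies are not recommended for this problem. Making home discharges the main denominator would change the Objective 2 population and would also drop patients who left against medical advice or have unknown disposition, who are not transfers. Adding disposition to the Cox models would not help, because those models start at the treatment index date, among patients who have already filled.

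The cost is one more stratified table from a field already planned for extraction, the sensitivity run, extra attrition counts and a sentence of text. Some transfer categories may have small cells.
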